Duration of IP administration	Once during surgery
Population	184 participants scheduled for total shoulder arthroplasty (TSA)
Study Sites	NYU Langone Orthopedic Hospital
Number of participants	184
Description of Study Agent/Procedure	Injection of 20mL 0.5% Bupivacaine HCL versus 10mL Liposomal Bupivacaine plus 10mL Bupivacaine 0.5% in an Interscalene block for TSA
Reference Therapy	Reference is Bupivacaine 0.5% for Interscalene block
Key Procedures	Interscalene nerve block with Liposomal Bupivacaine + Bupivacaine 0.5%
Statistical Analysis	Intention-to-treat analysis will be performed with mean, t-tests, within and between group ANOVA and linear regression,

CONFIDENTIAL

This material is the property of the NYU School of Medicine and Langone Medical Center. Do not disclose or use except as authorized in writing by the study sponsor

1 Key Roles

Principal Investigator:

[name]

Assistant Professor of Anesthesiology
Department of Anesthesiology, Perioperative care and Pain Medicine
NYU Langone Orthopedic Hospital
NYU Langone Health
[name]
[name]
[contact]

Co-Investigators:

[name]

Professor of Anesthesiology
Department of Anesthesiology, Perioperative care and Pain Medicine
NYU Langone Orthopedic Hospital
NYU Langone Health
[name]
[name]

[name]

Assistant Professor of Orthopedic Surgery
Department of Orthopedic Surgery
NYU Langone Orthopedic Hospital
NYU Langone Health
[name]
[name]

2 Background and Specific Aims

With the growing elderly population, the number of total shoulder arthroplasty (TSA) surgeries is increasing. Nationwide, the total and partial shoulder replacements increased from about 18,000 in 2000 to over 45,000 in 2013 according to the American Academy of Orthopedic surgeons (AAOS). One of the greatest drivers of cost following TSA has been shown to be discharge disposition. Effective pain control after surgery is paramount because it facilitates rehabilitation and decreases hospital length of stay. Additionally, it may increase the likelihood of patients being discharged to their home rather than a rehabilitation or skilled nursing facility.

TSA is a procedure that is well confined within the dermatomal distribution of an interscalene brachial plexus nerve block (ISB), making it an ideal procedure to both evaluate and compare the regional potential of varying agents. Although the analgesic coverage is typically ideal, single shot injection of the long acting

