3.1 Description of Study Design

PRE-SCREENING PHASE/CONSENTING PHASE:

Surgeons will inform eligible patients of the study during their pre-surgical visit in their office. The surgeons will use an IRB-approved recruitment flyer to help explain the study to the eligible patient. If the patient is agreeable, a member of the research team will provide further details and ask the patient to participate on day of surgery. Informed consent will be obtained on DOS when the patient is in the pre-operative holding room by an authorized research member.

BASELINE ASSESSMENTS:

After informed consent has been obtained, participants will complete a total of 3 PROMIS assessments (Upper Extremities, Pain Intensity and Global Physical Health) before undergoing their TSA surgery.

RANDOMIZATION PHASE:

Subjects scheduled to undergo TSA will be randomized to either the Bupivacaine 0.5% plus Liposomal bupivacaine Or Bupivacaine 0.5% group. Randomization of each subject will be done on day of surgery using randomization.com software to generate the assignment.

TREATMENT PHASE:

Subjects in the Bupivacaine plus Liposomal bupivacaine group will receive an interscalene nerve block with 10mL 0.5% Bupivacaine and 10mL of Liposomal bupivacaine. The control group will receive an interscalene nerve block with 20mL 0.5% Bupivacaine HCL. The anesthesiologist will NOT be blinded to what solution is being injected, as liposomal bupivacaine is a white fluid while bupivacaine is clear. All other stakeholders (patient, surgeon, other caregivers, and research staff collecting the data) will be blinded to the patient’s group assignment.

POST-OPERATIVE PHASE:

After initial recruitment, subjects’ pain will be assessed via visual analog scale (VAS) by nursing staff during the post-operative period as per standard of care. The VAS pain scores are collected and documented in the patient’s electronic medical record. Additionally, a standardized regimen of pain medication will be given to all subjects who are enrolled. The pain medications given to patients are standard of care medications and vary based on pain level. The clinical staff determines this for each patient.

CONFIDENTIAL

This material is the property of the NYU School of Medicine and Langone Medical Center. Do not disclose or use except as authorized in writing by the study sponsor

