Occupational and physical therapy progress and activity goals will be reviewed. As per standard of care, motor testing of the operated shoulder and arm will be assessed during these visits. This includes: No weight bearing exercises will be performed as per surgeon's instructions and the nursing staff will continue to obtain VAS pain scores.

[figure not shown]
During the 24-72 hour post-operative period, research staff will visit the patient while they are in the hospital to obtain and verify the pain medication taken. If the patient is discharged before the 72-hour period, the research staff will give the patient a copy of a medication record diary to complete. Additionally, the staff member will call the patient within 1-2 business days to obtain the remaining opioid utilization information.

After discharge, the research staff will continue to follow up with the patient on POD 7, POD 14 and POD 30 to assess pain scores, opioid usage patterns, and functional status. The pain intensity PROMIS assessment will be administered during each phone call. Additionally, on POD 30, participants will complete the Upper Extremity PROMIS form. Research staff will verify documented opioid refills through Epic and pharmacy records.

CONFIDENTIAL

This material is the property of the NYU School of Medicine and Langone Medical Center. Do not disclose or use except as authorized in writing by the study sponsor

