6.2 Analysis of Endpoints

Primary Endpoints:

Opioid utilization (expressed as oral morphine mg equivalents) used during initial 24-72 hours post-operative period after surgery.

Secondary Endpoints:

CONFIDENTIAL

This material is the property of the NYU School of Medicine and Langone Medical Center. Do not disclose or use except as authorized in writing by the study sponsor

Duration of opioid use
Patient reported pain scores (VAS)
Length of stay
Progress with physical therapy
Reported long-term narcotic use at home
Discharge location: home, acute rehab or skilled nursing facility
Documented opioid refills
Adverse events such as respiratory depression, hypoventilation, reintubation, nausea, constipation

The analysis of opioid use, VAS, and PROMIS assessments will rely on a univariate analysis of variance model for mean score. This model is in the class of models commonly known as unirep-ANOVA models. It assumes that the mean score is a function of elapsed time and the treatment regimen assigned. This model considers the fact that the subject's repeated measures are correlated. The fitted model will provide statistical estimates of the mean levels, the treatment-effect differences between mean levels, the standard deviation, the intra-class correlation coefficient, 95% CIs, standard errors (SE), and statistical hypothesis tests. The estimates of means will be used to compute summary criteria such as area under the curve (AUC) for each regimen. All estimates reported will be presented their 95% CIs.

All endpoints will be evaluated as fits the data set with graphical figures such as scatter plots, box-and-whisker plots, and frequency histograms to visualize the distribution of these outcomes and their relationships to covariates and treatment assignment. When appropriate descriptive graphical and tabular methods will also be estimated and presented in a graphical figure.

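### Section 6.2 models PROMIS on time and treatment only and does not say how the pre-operative scores enter; adjust each form for its own baseline and keep only post-operative values as outcomes

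*Combined protocol and SAP*

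**What the plan says.** Section 6.2 puts opioid use, VAS and PROMIS into one univariate repeated-measures ANOVA. On the mean structure it says: "It assumes that the mean score is a function of elapsed time and the treatment regimen assigned". It names no treatment-by-time term. From the fitted model it promises "the treatment-effect differences between mean levels", hypothesis tests and 95% confidence intervals, and it will use the estimated means to "compute summary criteria such as area under the curve (AUC) for each regimen".

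Section 3.1 gives the PROMIS schedule. At baseline, "participants will complete a total of 3 PROMIS assessments (Upper Extremities, Pain Intensity and Global Physical Health) before undergoing their TSA surgery". The follow-up calls are on POD 7, 14 and 30, and "The pain intensity PROMIS assessment will be administered during each phone call". In addition, "on POD 30, participants will complete the Upper Extremity PROMIS form". So Pain Intensity has one pre-operative and three post-operative values, and Upper Extremity has one of each. No repeat of Global Physical Health is described.

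No section names a baseline covariate. In 6.2 covariates appear only in the sentence on graphics, which are meant "to visualize the distribution of these outcomes and their relationships to covariates and treatment assignment". The Protocol Summary lists "within and between group ANOVA and linear regression" without saying what the regression adjusts for. Section 6.2.1 lists baseline data to be recorded and does not mention PROMIS.

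**The concern.** A pre-operative score on the same form is the natural covariate for a post-operative score. It is collected before the block is given, so adjusting for it is safe, and here it needs no new data. The stated model leaves it out.

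The text also leaves open whether the pre-operative form is one of the levels of elapsed time. This matters because randomised arms have the same expected score before surgery. A treatment main effect averaged over all time levels would then mix a visit that cannot show an effect with visits that can.

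What is at stake is the precision of the PROMIS comparisons and, on one reading, what their treatment estimate means. Several tests fit the present wording, and they differ widely in power.

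**Working it through.** **Inputs from the documents.** Section 4.6 gives 184 enrolled and 146 evaluable, an implied loss of 1 − 146/184 = 20.7%. Section 3 allocates 92 per arm, so an even split of the evaluable patients is 73 per arm. Section 6.3 states only the total, with no power, alpha, effect size or SD. There is therefore no power figure of the plan's own to reproduce.

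**Assumptions.** Two-sided 5% test, normal approximation, equal variance (1 SD²) before and after surgery, the same correlation r between any two time points, and 80% unadjusted power at a single post-operative visit. The last gives a reference effect of √(2/73) × (1.960 + 0.842) = 0.464 SD and a noncentrality of 2.80. The documents give no r; 0.3, 0.5 and 0.7 are used to show a range.

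**Upper Extremity (pre-operative and POD 30).** The wording admits three analyses. They are set against adjustment:

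- POD 30 only, pre-operative score unused: variance 1, noncentrality 2.80.
- Pre-operative score as a time level, treatment-by-time tested: with two time points this is the change score, variance 2(1 − r), noncentrality 2.80/√[2(1 − r)].
- Pre-operative score as a time level, treatment main effect tested: the effect is (0 + 0.464)/2 = 0.232 SD and the variance of the two-visit mean is (1 + r)/2, so the noncentrality is 1.40/√[(1 + r)/2].
- POD 30 adjusted for baseline: variance 1 − r², noncentrality 2.80/√(1 − r²).

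| Analysis | r = 0.3 | r = 0.5 | r = 0.7 |
|---|---|---|---|
| POD 30 only, unadjusted | 80% | 80% | 80% |
| Treatment-by-time (change score) | 66% | 80% | 95% |
| Main effect, pre-operative score as a time level | 41% | 37% | 33% |
| POD 30 adjusted for baseline | 84% | 90% | 97.5% |

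For example, the main effect at r = 0.5 has noncentrality 1.40/√0.75 = 1.62, giving 37%. The adjusted analysis has 2.80/√0.75 = 3.23, giving 90%.

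The adjusted variance is 0.91, 0.75 and 0.51 times that of POD 30 alone, and (1 + r)/2 = 0.65, 0.75 and 0.85 times that of the change score. Against the better of those two at each r, adjustment lowers the variance by 9%, 25% and 15%.

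**Pain Intensity (pre-operative, POD 7, 14 and 30).** With the pre-operative score as one of four time levels, a constant post-operative effect δ gives a main effect of (0 + δ + δ + δ)/4 = 0.75δ. Treatment-by-time is here a test on 3 degrees of freedom, so the change-score row above does not apply to this form. No adjusted power is tabulated for the three-visit mean, because it depends on how the follow-up visits correlate with each other as well as with baseline.

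**The case against.** The strongest reply is that an unadjusted randomised comparison is valid, that PROMIS appears in neither the Protocol Summary's nor section 6.2's endpoint list, and that no stated figure is wrong. All of this stands, and it sets the priority. It does not remove the point: 6.2 commits to modelling PROMIS and to hypothesis tests, and adjustment for a score already collected is the better method at almost no cost.

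It is also fair that the power figures are hypothetical. Section 2.2 expects the greatest benefit at 24 to 72 hours, so nothing in the documents supports 0.464 SD at POD 30. The figures compare analyses with one another; they do not forecast this trial's power.

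A reader might infer four stronger things that the documents do not support:

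- *The PROMIS comparison is biased.* Leaving out a baseline covariate does not bias it. Even on the main-effect reading there is no effect to dilute under the null hypothesis. What happens is that the estimate understates the post-operative difference. Nor does the plan say that this reading is the intended one.
- *No contrast is defined for any outcome.* For opioid use, 6.2 gives a post-operative window (24 to 72 hours, although the Protocol Summary has the initial 72 hours, which is a separate matter). For VAS, Aim 2 gives the initial 72 hours. The gap is mainly in PROMIS.
- *The primary endpoint loses material power.* Opioid use after surgery has no pre-operative counterpart, so Pain Intensity would be only a prognostic proxy. At an assumed r of 0 to 0.4, power by the same formula runs from 80% to 86%, a gain from nil to modest. The same proxy argument applies to VAS, for which no pre-operative score is described.
- *The single-visit gain carries over to the Pain Intensity mean.* If 0.464 SD is held fixed at each visit and r is equal throughout, the unadjusted three-visit mean already has 97%, 93% and 88% power at r = 0.3, 0.5 and 0.7, which leaves less room to gain.

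**Conclusion.** The point holds for PROMIS Pain Intensity and Upper Extremity. Section 6.2 does not use the pre-operative scores as covariates and does not say whether they are a time level. If they are unused, the cost is precision: at one visit, variance that could be lower by a factor of 1 − r². If they are a time level and the main effect is tested, the false-positive rate is intact but a constant post-operative effect is diluted to one half (Upper Extremity) or three quarters (Pain Intensity). The dilution fractions follow from the visit schedule alone. Every power figure rests on the assumed r, the assumed 80% reference and 73 per arm.

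Because PROMIS is in neither endpoint list, this is a low-priority improvement for the sponsor to consider.

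**What to change.** In section 6.2, before any by-arm data are seen:

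1. Use post-operative PROMIS values only as outcomes, with the patient's own pre-operative score on the same form as covariate.
2. Upper Extremity: ANCOVA at POD 30 with treatment and baseline. There is only one post-operative value, so no time term is fitted. The tested contrast is the adjusted treatment difference at POD 30.
3. Pain Intensity: a repeated-measures model over POD 7, 14 and 30 with treatment, time, treatment-by-time and baseline. The tested contrast is the mean treatment difference over the three visits.
4. Fill a missing baseline form with the overall baseline mean, computed blind to arm, so that adjustment drops no randomised patient.
5. Report the unadjusted estimate alongside.

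Adjusting the opioid total and VAS for pre-operative Pain Intensity is optional. If it is wanted, it should be named at the same time.

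The cost is a short paragraph and slight extra analysis work, with no new data and no patient burden. Rule 4 is needed only because adjustment would otherwise lose patients with a missing form. If the true correlation were zero, adjusting would cost almost nothing: in 20,000 simulated trials with 73 per arm, power was 78.9% adjusted against 79.2% unadjusted.

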14.3 Medication Usage Record

Medication Record for TSA Surgery

Thank you for participating in our research study and helping us improve pain control for patients undergoing total shoulder arthroplasty (TSA) surgery.

Patient: _____

Pain medication: **Percocet**

Please record the following information in the log below:

1. Time when you take your pain medication
2. How many pills you took at each time
3. Pain score on a scale of 0-10 (0 being no pain and 10 being the worst pain imaginable)
4. Any additional pain medications (such as Advil), therapies (such as ice packs) and side effects (such as itching or nausea).

Time	Number of pills of Percocet	Pain Score (scale of 0-10)	Additional pain medications, therapy or side effects

We will call you within 1-2 business days after surgery to ask for the above information. Additionally, participants can also scan, photograph and email the medication record to [name] at [contact]

Thank you for your participation.

CONFIDENTIAL

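### Between discharge and 72 h no pain score is requested at a set time independent of medication, so which scores feed the VAS means and AUC depends on opioid use or length of stay

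*Combined protocol and SAP*

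**What the plan says.** Aim 2 (Specific Aims) concerns pain in the first 72 hours, with VAS scores recorded both in hospital and after discharge. Section 2.2 expects the largest benefit between 24 and 72 hours.

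In hospital, section 3.1 says "pain will be assessed via visual analog scale (VAS) by nursing staff during the post-operative period as per standard of care", and "The VAS pain scores are collected and documented in the patient’s electronic medical record". The readable text sets no times or frequency.

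For a patient who leaves before 72 hours, section 3.1 says "the research staff will give the patient a copy of a medication record diary to complete", and that "the staff member will call the patient within 1-2 business days to obtain the remaining opioid utilization information". The diary in attachment 14.3 lists as its first item "Time when you take your pain medication", then the number of pills each time, then a "Pain score on a scale of 0-10 (0 being no pain and 10 being the worst pain imaginable"). A fourth item covers other medication, therapies and side effects. The form also mentions the call, which is to collect the diary contents.

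Later calls on POD 7, 14 and 30 assess pain, with the PROMIS Pain Intensity form each time.

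Section 6.2 treats mean score as a function of elapsed time and assigned regimen, with correlated repeated measures, and states: "The estimates of means will be used to compute summary criteria such as area under the curve (AUC) for each regimen". It gives no time grid, no AUC window and no rule for combining nursing VAS with diary scores. Section 6.1 says reasons for missing data will be documented, but gives no method for missing pain scores.

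**The concern.** From discharge to 72 hours, nothing in the readable text prompts a pain score from a patient who is comfortable and takes no medication. The patient who takes a pill has a row to fill in. Whether a score exists is therefore tied to the current pain level and to opioid use, which is the primary outcome. The moment when this source replaces the nursing record is set by length of stay, a secondary endpoint that section 2.2 says treatment may affect.

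If the new block works, the experimental arm may go home earlier and take fewer pills, and so lose more of its low scores. The 24-72 hour pain comparison would then be made on readings partly selected by the treatment effect. A model with only elapsed time and regimen averages the scores that exist and has no term for why the others do not.

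**Working it through.** **1. Which scores exist in the Aim 2 window.**

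| Period | Source in the readable text | Set time? | What produces a score |
|---|---|---|---|
| Surgery to discharge | Nursing VAS in the medical record (3.1) | None stated | Ward routine |
| Discharge to 72 h | Diary, 0-10 score (3.1, 14.3) | None | Mainly taking a pill; other entries possible |
| 1-2 business days | Phone call (3.1, 14.3) | No pain time stated | Collects opioid use or diary contents |
| POD 7, 14, 30 | Phone calls (3.1) | Fixed days | Independent of stay and pills, but after 72 h |

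**2. Two readings of the plan.** If diary scores enter the VAS analysis, scores after discharge are selected by medication use. If they do not, scores stop at discharge. In both cases the set of observed scores depends on something treatment may change.

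**3. Illustration of the first reading.** The plan has no figure to reproduce here: it states 184 enrolled and 146 evaluable, but no pain SD, stay or pill rate. Every input below is an assumption.

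- 40,000 simulated patients per arm, scored every 4 h from 0 to 72 h, limited to 0-10.
- Mean pain at time t: 1 + 4/(1 + exp(-(t - d)/3)) - 0.02 × max(t - d, 0). Block duration d is normal, mean 18 h, SD 5 h.
- Between-patient SD 1.5, within-patient SD 1.2. The treatment effect, where present, is a shift of -1 before limiting to 0-10.
- Discharge time normal with SD 8 h, limited to 18-72 h, independent of the patient's own pain.
- A score y is seen if the patient is in hospital or takes a pill. Pill probability is 1/(1 + exp(-s(y - 5))), with s = 0.5, 1.0 or 1.5.
- Summary: mean of the observed scores at each time, trapezoid area over 24-72 h, divided by 48.

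Differences are experimental minus control, for s = 0.5 / 1.0 / 1.5:

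| Scenario | True mean difference | Observed mean difference | Observed AUC difference (point-hours) |
|---|---|---|---|
| No effect, stay 36 h in both arms | -0.03 / 0.01 / 0.01 | -0.03 / 0.00 / 0.02 | -1.5 / 0.1 / 0.8 |
| No effect, stay 30 h vs 48 h | 0.01 / 0.00 / 0.00 | 0.33 / 0.50 / 0.59 | 15.9 / 24.2 / 28.2 |
| Effect, stay 36 h in both arms | -0.96 / -0.98 / -0.98 | -0.91 / -0.81 / -0.73 | -43.4 / -38.8 / -35.0 |
| Effect, stay 30 h vs 48 h | -0.98 / -0.97 / -0.99 | -0.58 / -0.25 / -0.09 | -27.7 / -11.8 / -4.1 |

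The true AUC differences in the two effect rows lie between -46.1 and -47.3.

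**4. Share of the effect lost.** Equal stays: 1 - 0.91/0.96 = 5%, 1 - 0.81/0.98 = 17%, 1 - 0.73/0.98 = 26%. Unequal stays: 1 - 0.58/0.98 = 41%, 1 - 0.25/0.97 = 74%, 1 - 0.09/0.99 = 91%.

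**5. With fixed-time scores for everyone**, observed and true values coincide by construction: -0.96 to -0.99 points, or -46.3 to -47.6 point-hours.

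**6. Limits.** The simulation pools nursing and diary scores as one scale, allows no diary rows without a pill, and uses raw means at each time instead of a fitted repeated-measures model. The second reading was not simulated. There the direction rests on the plausible assumption that patients with less pain leave sooner.

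**The case against.** Several stronger readings are tempting, and the documents do not support them.

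- **That nursing scores are unscheduled.** The text says only that they follow routine care. Ward practice may have a timetable, and a figure in section 3.1 and the schematic in 3.2 are not shown.
- **That the diary is filled only when a pill is taken.** This is inferred from the layout. The fourth item permits rows without Percocet, though nothing asks for a score in their absence.
- **That all pain data depend on stay and opioid use.** Patients still in hospital are scored by nurses whether or not they take opioids, and the POD 7, 14 and 30 calls depend on neither. Those calls cannot supply a 0-72 h profile: the PROMIS worst and average items look back over 7 days on a five-level scale.
- **That the plan pools diary scores with nursing VAS.** No section says so. The source of VAS after discharge is undefined, which is why both readings are considered above.
- **That irregular times alone invalidate the model or AUC.** A model in elapsed time can use irregular times. The difficulty is observation that depends on the outcome.
- **That most of the effect disappears.** Suppose scores are normal with SD 2 and means 4 and 3, and are logged only at or above level 4. The recorded mean is m + 2φ(a)/(1 - Φ(a)) with a = (4 - m)/2, giving 5.596 and 5.282. A true difference of 1.0 becomes 0.31 (0.42 at level 3, 0.23 at level 5). This is a worst case, with a hard threshold and no nursing scores.

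It is also fair to say that VAS is secondary and that equal stays with no true effect produce no material spurious difference. All of this narrows the point. What stands is that no readable text asks for a set-time, medication-independent score between discharge and 72 h, and no method for missing VAS is given.

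**Conclusion.** The point holds for the interval from discharge to 72 hours. In that interval the availability of pain scores depends on medication use or length of stay, and the analysis in section 6.2 does not address this. The likely direction is to hide a benefit of the experimental block.

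The size cannot be derived from the documents. Under the stated assumptions, and if diary scores are pooled with nursing scores, attenuation is modest to moderate with equal stays (5% to 26%) and large (41% to 91%) if mean stay differs by 18 h (30 h against 48 h). In that last case a spurious difference of 0.33 to 0.59 points against the experimental arm also appears when there is no true effect. The 18 h gap is an assumption, and a smaller gap would be expected to matter less. The primary opioid endpoint is not touched by this point.

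**What to change.** Add diary rows at fixed times, for example 24, 36, 48, 60 and 72 h counted from the injection, each asking for a 0-10 score whether or not a pill was taken. For patients still in hospital, use the nursing score nearest each time within a stated window, for example plus or minus 3 h. The 72 h row requires the call, or return of the form, to come after 72 h; the form's wording of 1-2 business days after surgery can fall earlier.

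In section 6.2, state that the pain comparison and AUC cover 24-72 h and use these times only. If a 0-72 h AUC is wanted, add fixed times before 24 h, because the times above cannot support it. State how nursing VAS and diary 0-10 scores are combined and how a missing fixed-time score is handled. Keep scores logged at pill-taking as descriptive.

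The cost is up to five extra self-scores per patient, a few lines on the form and a few sentences of analysis text. Section 14 lets attachments change without a protocol amendment, though section 9.2 sends participant materials to the IRB. The section 6.2 text would need an amendment. This is a cheap improvement.
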